### **3.2.3. REMOVAL OF SUBJECTS FROM THERAPY OR ASSESSMENT**

#### **3.2.3.1. CRITERIA FOR WITHDRAWAL OF SUBJECTS FROM STUDY**

Participation in the study is strictly voluntary. A subject has the right to withdraw from the study at any time, for any reason.

Subjects who terminate study participation for reasons of lost to follow-up, informed consent withdrawal, or death will not have any follow-up assessments.

In the event a subject is discontinued from the study, the study monitor and the Sponsor will be informed immediately.

#### **3.2.3.2. SUBJECT DISCONTINUATION CRITERIA**

The subject discontinuation criteria are described below:

##### **Efficacy discontinuation criteria at a Week 12, 16 or 20:**

Any subject with < 20% improvement from baseline in both swollen and tender joint count (SJC and TJC; 66/68 counts) at any of the visits at week 12, 16 or 20 will discontinue from the trial, but remain blinded to study drug assignment. The visit at which subjects will meet the efficacy discontinuation criteria, is defined as the Early Termination Visit for these patients. Subjects who have to discontinue study drug but are not withdrawing consent for post-treatment follow-up, should return for the Follow-up Visit, planned 12 weeks after the last study drug administration, according to section 3.4.1.3.

##### **Study drug must also be permanently discontinued if any of the following occurs:**

- Serious hypersensitivity reaction.
- Following abnormalities in laboratory test results: ALT and/or AST elevations between > 3 and  $\leq$  5 x ULN (confirmed by repeat testing on 2 consecutive visits),

ALT or AST elevations  $> 5 \times$  ULN, absolute neutrophil count  $< 1 \times 10^9/L$ , or a platelet count  $< 50 \times 10^3/\mu L$ .

- Diagnosis of or suspicion of a serious infection (requiring parenteral antibiotic and/or hospitalization) or TB.
- Malignancy.
- Pregnancy or pregnancy planned within the study period.
- Demyelinating disease.
- The initiation of protocol-prohibited medications (see section [3.3.6](#)).
- Congestive heart failure (CHF) class III or IV as defined by the New York Heart Association, unstable angina pectoris, myocardial infarction, cerebrovascular accident.
- In case of interruption of study drug administration for 2 consecutive doses.
- The randomization code is broken prematurely by the Investigator or his/her staff.
- The Investigator or the Sponsor's medical monitor deems it is in the subject's best interest.

Discontinuation of study drug must be considered for subjects who develop a severe study drug injection-site reaction or a severe hypersensitivity reaction.

Subjects who have to discontinue according to these criteria but are not withdrawing consent for post-treatment follow-up should return for the Early Termination Visit planned 2 weeks after the last study drug administration (unless they discontinue during a study visit, in which case that becomes their Early Termination Visit). Subjects should also have a Follow-up Visit planned 12 weeks after the last study drug administration, according to section [3.4.1.3](#).

A description of assessments to be performed for subjects who discontinue from the study is provided in section [3.4.1.3](#) (also see Early Termination Visit in the [Schedule of Assessments](#)).

For all subjects, every effort should be made to contact the medical monitor prior to discontinuing study drug, where medically feasible. If there is a medical reason for discontinuation, the subject will remain under the supervision of the Investigator until satisfactory health has returned unless the subject withdraws his consent and is no longer willing to come to the visits. Subjects who discontinue will not be replaced.

### **3.2.3.3. STUDY TERMINATION**

If the Sponsor abandons the study prior to commencement of any protocol activities, and after IEC/IRB and Competent Authority (CA) approvals have been

---

received, the Investigator or Sponsor must notify the IEC/IRB and CA by letter outlining the reasons for abandonment of the study.

At any time during the study, the Sponsor may suspend or terminate the study or part of the study for any reason. If the Investigator suspends or terminates participation in the study, the Investigator will promptly inform the Sponsor and the IEC/IRB and provide them with a detailed written explanation. The Investigator will also return all study drug, study drug containers, and other study materials to the sponsor.

Upon study completion, the Sponsor will provide the Investigator, IEC/IRB, and CA with final reports and summaries as required by regulations.

In case of suspension or halt due to safety reasons, the CA and IEC/IRB will be notified immediately and at the latest within 15 days after the study is halted, clearly explaining the reasons, and describe follow-up measures if any, taken for safety reasons.

### **3.3. TREATMENT OF SUBJECTS**

For an overview of the treatments to be administered, please refer to section [3.1](#).

#### **3.3.1. IDENTITY OF STUDY DRUG**

- Study drug:
  - Active substance: ALX-0061 Nanobody.
  - Activity: ALX-0061 Nanobody binds to the IL-6R and inhibits the interaction between the IL-6 ligand and the receptor subunit, thereby preventing receptor signaling.
  - Pharmaceutical formulation: [REDACTED]  
[REDACTED]  
[REDACTED]  
[REDACTED]  
[REDACTED] ALX-0061 will be supplied as a sterile liquid for s.c. injection at a volume of 0.5 mL or 1.0 mL in pre-filled single-use syringes. No preservatives are present.
  - Route and volume of administration: s.c. injections at a volume of 0.5 mL and/or 1.0 mL.
- Placebo:
  - Substance: placebo.
  - Activity: none.
  - Pharmaceutical formulation: [REDACTED]  
[REDACTED]  
[REDACTED] Placebo will be supplied as a sterile liquid for s.c. injection at a volume of 0.5 mL or 1.0 mL in pre-filled single-use syringes. No preservatives are present.
  - Route and volume of administration: s.c. injections at a volume of 0.5 mL and/or 1.0 mL.

The sponsor will be providing adequate supplies of ALX-0061 and placebo for this study.

Details on study drug allocation and dosing are provided in section [3.1.1](#).

### **3.3.2. OTHER MEDICATION ADMINISTERED IN THE STUDY**

Stable dose and route of MTX (12.5-25 mg weekly) maintained during the 6 consecutive weeks prior to screening and for the duration of the study. The concomitant medication dose may be reduced or temporarily discontinued because of abnormal laboratory values, side effects, concurrent illness, or the performance of a surgical procedure, but the change and reason for the medication should be clearly documented in the subject's medical record and in the electronic case report form ([e]CRF).

Commercially available MTX will be used in this study and will not be provided by the Sponsor.

It is mandatory that all subjects should receive at least 5 mg oral folic acid or oral folinic acid weekly.

Subjects who will meet the efficacy discontinuation criteria (see section 3.2.3.2) will discontinue from the trial and any future care will then be provided (outside of the study) at the discretion of the treating physician as part of usual clinical practice.

### **3.3.3. DRUG ACCOUNTABILITY**

The Pharmacist or his/her designee is responsible for acknowledge receipt of each shipment of study drug and will verify the condition and quantity of the study drug.

The study drug will be kept in a locked and secured storage facility accessible only to those authorized by the Investigator to dispense the study drug.

The responsible person will keep an inventory. This will include a description of the formulation and the quantity of study drug received for the study and a record of the materials that are dispensed, to whom and when.

On termination of the study, the pharmacist, the Investigator and/or designated personnel will conduct a final inventory of the study drug supply and will record the results of this inventory in the Drug Accountability Form. All study drug supplies will be returned to and destroyed by a vendor upon Sponsor approval, or will be locally destroyed according to site procedure upon Sponsor approval.

Instructions for drug accountability are available in the Study Drug Manual and the IWRS Instruction Manual.

### 3.3.4. STUDY DRUG HANDLING

Instructions for study drug administration, handling, and storage, are available in the Study Drug Manual and the IWRs Instruction Manual.

#### **Packaging and Labeling**

The study drug will be labeled in accordance with local regulations. Each label will contain but will not be limited to, study number, storage conditions, dosing instructions, sponsor's name, address, and telephone number.

One kit will contain 2 syringes. A randomization system will assign each of the treatment kits to a subject. The content of each treatment kit will be determined according to the randomization schedule.

#### **Storage**

Study drug will be provided under refrigerated conditions and must be stored in a secure, limited-access location under the storage conditions specified by the Sponsor.

Active ALX-0061 and placebo must be refrigerated at 2°C to 8°C (35.6 °F to 46.4 °F), and should be stored in the secondary packaging until administration. It should not be frozen or shaken.

Site storage conditions should be monitored by the site personnel and reviewed by the monitor during site visits. Deviations from the storage requirements must be documented and reported to the Sponsor, according to the instructions provided in the Study Drug Manual.

#### **Dispensing**

The Investigator or qualified designee(s) will dispense study drug to subjects who have met the entry criteria. Clinical supplies may not be used for any purpose other than that which is stated in this protocol.

#### **Product Quality Complaint**

Any malfunctioning pre-filled syringe has to be communicated (written or electronically) and returned to the Sponsor or its designee.

### 3.3.5. STUDY DRUG INJECTIONS

ALX-0061 s.c. or placebo s.c. injections, as applicable, will be administered using the single-use pre-filled syringe at the site under the supervision of an appropriate licensed and authorized health professional at all visits.

All subjects are to receive 2 injections in the abdominal region in succession at each dosing day. Each injection should be given at a different quadrant in the abdominal region. As injections are to be performed q2w, all injections can be performed in an abdominal quadrant of choice. However, note that the area of administration needs to be evaluable for local skin reaction (normal skin without skin burns, scars, or large tattoos in the area of administration). The abdominal regions used for the administrations will be recorded in the (e)CRF. All subjects will remain at the site for 60 minutes after the injection in order to assess potential adverse reactions.

Detailed instructions for study drug administration are available in the Study Drug Manual.

No constraints with regard to timing of study drug administration during the day of dosing are to be taken into account. The exact times of study drug dosing at the clinical site will be recorded in the (e)CRF.

### 3.3.6. PRIOR AND CONCOMITANT THERAPY

Prior and concomitant medication are documented throughout the study.

Prior medications as per in- and exclusion criteria are detailed in section [3.2](#).

During the screening and 24-week treatment and assessment period of the study, subjects are not allowed to initiate DMARDs other than MTX for RA (see permitted and prohibited medication below).

#### Permitted Medication

Stable dose and route of MTX (12.5-25 mg weekly) maintained during the 6 consecutive weeks prior to screening and for the duration of the study. The concomitant medication dose may be reduced or temporarily discontinued because of abnormal laboratory values, side effects, concurrent illness, or the performance of a surgical procedure, but the change and reason for the medication should be clearly documented in the subject's medical record and in the (e)CRF.

Subjects treated with NSAIDs (including aspirin and selective cyclooxygenase 2 inhibitors) and other analgesics (except high-potency opioid analgesics, such as World Health Organization [WHO] class IV drugs [e.g., morphine; see prohibited

medication]) should receive the usual marketed doses approved in the country in which the study is being conducted and should be on a stable dose from at least 2 weeks prior to screening until the Week 24 Visit, or until the Early Termination Visit. Changes in the dose may be done at the discretion of the Investigator if the subject develops unacceptable side effects. Whenever possible, short-acting NSAIDs and other analgesics should not be administered within 6 hours before study assessments. Long-acting ones can be maintained at their usual dosing intervals before study assessments.

Subjects treated with oral corticosteroids should receive a stable dose equivalent to  $\leq 10$  mg of prednisone/day, for at least 2 consecutive weeks prior to screening, and continue this dose up to and including Week 24, or until the Early Termination Visit. The dose of oral corticosteroid may be decreased at the discretion of the Investigator only if the subject develops unacceptable side effects.

The number of intra-articular corticosteroid injections is limited to 2 injections over a 24-week period. Intra-articular injections may not be given from Week 8 until Week 12. The joint(s) affected by the procedure(s) will be considered as swollen and tender for 28 days/4 weeks in the data analyses from the date of the procedure onward.

The expression of hepatic CYP450 enzymes is suppressed by IL-6. IL-6 blocking might therefore influence (normalize) CYP450 expression and products that are substrates for CYP450 enzymes (e.g., statins, warfarin, theophylline, oral contraceptives, calcium antagonists, phenytoin, cyclosporine, benzodiazepines) could be metabolized faster. Subjects taking medicinal products which are metabolized via CYP450 3A4, should be closely monitored and their treatment might have to be adapted if necessary in order to maintain therapeutic efficacy. Subjects on warfarin will be monitored by assessment of INR (See [Schedule of Assessments](#)); the lipid levels will be evaluated which will be of help to monitor the subjects on statins (See [Schedule of Assessments](#)). If needed, the Investigator or the relevant treating physician should adapt the treatment of the concerned subject (unscheduled visits can be planned upon the discretion of the treating physician). Given the long half-life of ALX-0061, the influence on the hepatic enzymes can persist for several weeks.

Other medication (e.g., to treat AEs) may only be prescribed after consultation with the Investigator, unless in case of an emergency situation that does not allow discussion.

## Prohibited Medication

The following medications are prohibited during the study (up to and including Week 24 or Early Termination Visit):

- DMARDs other than a stable background dose of MTX.
- i.m or i.v. administration of corticosteroids for the treatment of RA. Any increase in oral corticosteroids above the baseline. For intra-articular dosing see "permitted medication".
- High-potency opioid analgesics, including but not limited to hydrocodone, metopon, oxycodone, clonitazene, hydromorphone, oxymorphone, morphine, fentanyl, levorphanol, buprenorphine, methadone, meperidine.
- Use of any biologic DMARD, targeted synthetic DMARD (such as tofacitinib), or investigational drugs.
- Use of any live attenuated vaccine.

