#### **Pharmacodynamics**

- All ALX-0061 groups received biologically effective doses: rapid and long-lasting increases in IL-6 and sIL-6R concentrations were observed across all ALX-0061 dose groups. The PD results confirmed that sIL-6R (and IL-6) concentrations can be used as a biomarker for target engagement by ALX-0061.

- Dosing q4w at 3 mg/kg yielded the highest exposure, as indicated by the observed average trough levels (~ 10 µg/mL), strongest biomarker response (based on sIL-6R profile), and the highest clinical remission rates.

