#### **1.2.5. BENEFITS AND RISK ASSESSMENT**

Although a number of treatment options are available for RA, there remains a clear need for novel therapeutics. Many patients do not benefit optimally from the available small molecule and biologic drugs, leaving opportunity for differentiated drugs with new modes of action and an improved safety profile.

Considering the importance of IL-6 in chronic inflammatory diseases, several companies are developing drugs that target this pathway, and multiple clinical

studies have demonstrated that treatment with IL-6 pathway inhibitors can improve manifestations of RA. ALX-0061, administered i.v. and in combination with MTX, has been shown to be effective in reducing signs and symptoms for the treatment of subjects with active RA.

The current study is designed to evaluate the efficacy and safety of ALX-0061, administered s.c. in subjects with moderate to severe active RA. Potential candidates for this study are required to have objective evidence of active disease, and have had an inadequate response to methotrexate.

The Sponsor is studying s.c. administration in an effort to develop a route of administration which will offer an alternative and more convenient option for administration, while maintaining its clinical efficacy and safety profile. Details on the design of, and rationale for, the current study are available in section [3.1.1](#) of the protocol.

An assessment of potential risks associated with inhibition of the IL-6 pathway, or inherent to the administration of therapeutic proteins, is described below. IL-6 is a pleiotropic cytokine with an important role in a broad spectrum of biological events, therefore, potential risks related to inhibition of the IL-6 pathway, as well as potential risks inherent to the administration of therapeutic proteins, are considered.

- Inhibition of the IL-6 pathway has immunomodulatory effects, and has been reported to increase the risk for infection [\[15, 16\]](#). So far, serious infections have not been reported for ALX-0061.
- Suppression of IL-6 activity is known to reduce the levels of acute phase proteins such as CRP, SAA and fibrinogen [\[17, 18\]](#).
  - Rapid and long-lasting decreases in CRP, ESR, fibrinogen and SAA were observed across all ALX-0061 dose groups in study ALX-0061-1.1/10. In general, these pharmacological effects were reversible and associated with clinical response in signs and symptoms of RA.

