In view of the early stage of development, it is not established whether the above mentioned effects would constitute clinically meaningful risks for administration of ALX-0061; additional clinical studies are needed for further evaluation. In general, the pharmacological effects reported during Study ALX-0061-1.1/10 were reversible and associated with clinical response in signs and symptoms of RA. For additional and more detailed information regarding ALX-0061, the investigator is referred to the current Investigator's Brochure.

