12. Have received intra-articular (i.a.), intramuscular (i.m.), or i.v. corticosteroids during the 4 weeks prior to screening.

13. Have received approved or investigational biological or targeted synthetic DMARD therapies for RA (including TNF  $\alpha$  inhibitors, abatacept, rituximab, or Janus kinase [JAK]-inhibitors) less than 6 months prior to screening. For subjects who received prior rituximab, subjects with an inadequate recovery of B cells should be excluded regardless of when they received rituximab.
14. Have a history of toxicity, non-tolerance, primary non-response or inadequate response to a biological therapy, or targeted synthetic DMARDs (including JAK inhibitors), for RA.
15. Have received prior therapy blocking the IL-6 pathway, such as but not limited to ALX-0061, sirukumab, sarilumab, clazakizumab, olokizumab, tocilizumab (TCZ) at any time, will be excluded.
16. Have a known hypersensitivity to the active product or any excipient of the study drug.
17. Abnormality in screening laboratory test results:
  - a. ALT and/or AST levels  $\geq$  1.5 times the ULN.
  - b. Hemoglobin levels  $\leq$  85 g/L (8.5 g/dL).
  - c. Platelet count  $\leq$   $125 \times 10^9/L$  (125,000 cells/mm $^3$ ).
  - d. White blood cell count  $\leq$   $3.5 \times 10^9/L$  (3,500 cells/ mm $^3$ ); neutrophils:  $\leq 2 \times 10^9/L$ .
  - e. Serum creatinine levels  $\geq$  1.5 mg/dL (133  $\mu$ mol/L).
  - f. Any other clinically significant abnormal screening laboratory results as evaluated by the Investigator.
18. Positive screening for hepatitis B, hepatitis C, or HIV.
19. At the discretion of the treating physician, subjects with impaired cellular or humoral immunodeficient (i.e., Ig deficiency, IgA, IgG etc.) disorders should be excluded.
20. History or presence of alcohol or drug abuse.
21. Blood donation ( $> 500$  mL) or a blood loss of comparable volume within 3 months prior to first dosing.
22. Planned donation of germ cells, blood, organs, bone marrow during the course of the study or within 6 months thereafter.
23. Male with female partner who is planning to become pregnant within 6 months of last dosing.
24. Pregnant women or female subjects who are breastfeeding.
25. History of anaphylactic reaction.
26. Administration of a live, attenuated vaccine within 3 months before dosing with ALX-0061, or anticipation that such a live attenuated vaccine will be required during the study or within 6 months after last dosing.

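### The live-vaccine ban ends at Week 24 or Early Termination, at about the on-treatment trough, and is not carried through the safety follow-up

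*Combined protocol and SAP*

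**What the plan says.** The Prohibited Medication list in section 3.3.6 opens with "The following medications are prohibited during the study (up to and including Week 24 or Early Termination Visit", and its last entry is "Use of any live attenuated vaccine". The other four entries are additional DMARDs, systemic corticosteroids or oral increases, high-potency opioids, and biologic, targeted synthetic or investigational drugs. All five share the one end date.

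Live vaccines appear in one other place, exclusion criterion 26 (section 3.2.2). Besides recent vaccination, it excludes subjects with "anticipation that such a live attenuated vaccine will be required during the study or within 6 months after last dosing". Section 3.2.2 is a list of conditions for enrolment.

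Subjects who do not enter the extension return for a Follow-up Visit 12 weeks after their last injection (Synopsis, Study Duration; section 3.4.1.3). Concomitant medication is recorded to the last visit (section 3.4.1). For anything not on the prohibited list, section 3.3.6 (Permitted Medication) says: "Other medication (e.g., to treat AEs) may only be prescribed after consultation with the Investigator", with an exception for emergencies.

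**The concern.** Ending at Week 24 suits drugs that would disturb the efficacy assessments, because efficacy is followed only to that visit. A live-vaccine restriction is more naturally tied to how long the drug remains in the body. The protocol gives no reason for either vaccine window, so that is an inference.

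If it is right, the ban stops while drug is still present, and a subject with an unforeseen need could be vaccinated early in washout without breaching the protocol. What is at stake is subject safety. Section 1.2.5 says: "Inhibition of the IL-6 pathway has immunomodulatory effects, and has been reported to increase the risk for infection".

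**Working it through.** **1. The plan's own timeline.** The last injection is at Week 22 and the Follow-up Visit is 12 weeks later: 22 + 12 = Week 34, as the Synopsis states. From Week 24 to Week 34 is 10 weeks (70 days).

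**2. Time since active drug when the ban lifts** (dosing weeks from section 3.1.2).

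| Arm | Last active dose | Days to Week 24 | Dosing interval |
|---|---|---|---|
| 150 and 225 mg q2w | Week 22 | 14 | 14 |
| 75 and 150 mg q4w | Week 20 (Week 22 is placebo) | 28 | 28 |

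Week 24 is thus a trough time in every active arm. So are the efficacy exits at Weeks 12, 16 and 20, because assessments precede dosing (Schedule of Assessments, footnote A).

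**3. Is the Week 24 level equal to earlier troughs?** Add the contributions of all doses, each decaying as 2^(−t/half-life), with instant absorption. The documented half-life is about 15 days, from linear clearance alone (section 1.2.4.1, Pharmacokinetics). In units of one dose:

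- q2w, Weeks 20, 22, 24: 1.098, 1.098, 1.099.
- q4w, Weeks 16, 20, 24: 0.376, 0.377, 0.378.

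With assumed half-lives of 7 and 19 days the levels differ, but Week 24 still matches the earlier troughs: q2w 0.333 throughout, or 1.491, 1.495, 1.497; q4w 0.067 throughout, or 0.553, 0.559, 0.561.

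**4. Exits for other reasons.** Early Termination is normally 2 weeks after the last injection (section 3.2.3.2). In the q4w arms that injection may be active or placebo, so the gap from active drug is 14 or 28 days, or longer if doses were missed. At 14 days the level is 2^(14/15) = 1.9 times trough (4.0 times at an assumed 7-day half-life).

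**5. Washout after Week 24.**

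- Left at Week 34, as a share of the Week 24 level: 2^(−70/15) = 0.039, about 4%. For assumed half-lives of 7 to 19 days the range is 0.1% to 8%.
- Time to fall to 10% of the Week 24 level: 15 × log2(10) = 50 days (23 days at a 7-day half-life).
- Six months after a Week 22 dose is about Week 22 + 26 = 48, which is 14 weeks beyond Week 34. At the 15-day half-life about 0.04% (q2w) or 0.08% (q4w) of the Week 24 level would then remain, counting about 182 days from the last active dose.

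**6. Is the trough pharmacologically active?** For the earlier i.v. study, section 1.2.4.1 reports: "Dosing q4w at 3 mg/kg yielded the highest exposure, as indicated by the observed average trough levels" (about 10 µg/mL), with the strongest biomarker response. As a rough comparison, take the 82.3% s.c. bioavailability (section 1.2.4.2) and an assumed weight of 60 to 90 kg:

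- Reference dose per 4 weeks: 3 × 60 = 180 mg to 3 × 90 = 270 mg.
- q2w arms: 0.823 × 300 = 247 mg and 0.823 × 450 = 370 mg. Ratios run from 247/270 = 0.9 to 370/180 = 2.1.
- q4w arms: 0.823 × 75 = 62 mg and 0.823 × 150 = 123 mg. Ratios run from 62/270 = 0.2 to 123/180 = 0.7.

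Active troughs are likely in the q2w arms and uncertain in the q4w arms. Clearance is nonlinear, so dose ratios do not convert directly into trough ratios.

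**7. Does any other text restore the restriction?** Section 3.4.1 records a vaccine but does not bar it. Sections 3.2.3.2 and 3.4.1.3 add visits without extending the ban. The consultation rule leaves the decision to the Investigator. After an efficacy exit, section 3.1.1 places further care outside the study with the treating physician, so it is unclear how far that rule reaches.

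**The case against.** A reader might infer that exclusion 26 and the prohibited list contradict each other. They do not. One screens foreseeable need at entry and the other restricts conduct on study, and both can be obeyed.

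Exclusion 26 already removes most of the risk. What remains is an unforeseen need, in a subject who does not enter the extension, in an active arm, within a few weeks. For that, consultation is mandatory outside emergencies and has no Week 24 end date. Section 4.2 makes the Investigator responsible for care throughout the study, and section 3.2.3.2 keeps subjects who stop for medical reasons under supervision. This cover is real, though it falls short of a prohibition.

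A reader might also infer that vaccination at trough has been shown to be unsafe. No passage says so. Section 1.2.5 adds "So far, serious infections have not been reported for ALX-0061" and, of the listed class effects, "it is not established whether the above mentioned effects would constitute clinically meaningful risks for administration of ALX-0061". The biomarker response shows target engagement, not impaired handling of a live vaccine. The exposure figures also lean on assumptions and on a half-life that applies only at high concentrations.

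Finally, advice on vaccines may sit in the consent form or the Investigator's Brochure. Consent pages were removed from this file, and neither the Brochure nor the extension protocol was available, so subjects cannot be said to have been left without guidance. These objections limit the weight of the point. They do not supply a reason for ending the vaccine ban at Week 24.

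**Conclusion.** The point holds as a low-frequency subject-safety matter. The timing result is firm: at Week 24 and at efficacy exits the ban lifts at about trough, whichever half-life between 7 and 19 days is used. At some other-reason exits in the q4w arms it may lift above trough.

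The clinical consequence is inferred from class infection risk. The documents give neither a rate of unforeseen vaccine need nor a number entering the extension, so no count of affected subjects is offered. Endpoint, power, alpha and the efficacy analyses are unaffected.

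Exclusion 26 might suggest that the ban must run to 6 months. The washout figures do not require that: most of the exposure at issue lies between Week 24 and Week 34, and little remains in the 14 weeks after that. A 6-month ban is optional.

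**What to change.** Give live attenuated vaccines their own line in the Prohibited Medication list, barred through the Follow-up Visit (12 weeks after the last injection of study drug), and state that subjects who enter the extension follow that protocol. Leave the other four entries and their end date unchanged.

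This adds no visit or procedure. The cost is a longer restriction, 34 − 24 = 10 weeks beyond Week 24, and it falls on placebo subjects too because assignment stays blinded. If the sponsor prefers 6 months, the restriction would run 48 − 24 = 24 weeks beyond Week 24. The part after the last visit would have to be worded as a subject obligation, as section 3.3.6 does for contraception, and no study visit would check it.
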